## 6) Study Procedures & Schedule of Events

The multi-component educational intervention includes the following:

Training:

*Group Training:*

Group training sessions will consist of an initial training and an one hour follow up refresher training on how to use the SKILP device and identifying Melanoma. The in-person trainings are designed as lunch and learn sessions. The initial training will include how to use the MTED, how to use a SKILP dermoscopy device, how to use the Epic health maintenance reminder tool to document a high-risk patient, and how to triage. We will support workflow restructure to involve use of Epic tools, SKILP devices, etc. but are unable to assess changes to workflow itself. PCPs will receive education on how to use a collection of skin cancer-specific SmartPhrases in Epic. These SmartPhrases contain resources such as a melanoma risk stratification tool, skin cancer after visit summary, and templates for biopsies and skin exams. An accompanying PowerPoint document explains how to access and use the SmartPhrases, as well as provides instructions on how to satisfy billing codes and health maintenance reminders. The training is tailored to PCPs but may be delivered to the entire healthcare team (nursing staff and medical assistants) to facilitate implementation.

The follow up refresher training will follow the same format as the initial training and will contain similar content as the initial training (See Dermoscopic Red Flags of Melanoma Powerpoint in Supplemental Materials).

Live trainings may be in-person or virtual, but will not be recorded. We will use a sign-in sheet to collect names and email addresses of those who attended the in-person trainings so that we may follow up with them and provide a link to the online portion of the trainings and to measure expose of the training.

Lunches will be provided at all group training sessions, along with SKILP devices at the intial training and educational materials. Pre- and post-training tests will be given during the initial in-person training session to measure uptake of the training. These tests will be distributed through an email about the upcoming training (see supplemental materials) and a QR code that

participants can access through their phones or laptops during the training. A pre-recorded version of the trainings will also be available to accommodate busy schedules.

*Refresher trainings:*

For those that complete the initial training we will offer short refresher trainings via a series of 5 emails that contain refresher material from the initial training and will be designed to increase practice and repetition of identification of skin-related pathologies. Emails will include a link to a short Qualtrics survey to measure uptake of training information.

We will email all participants of the intial training and offer the refresher materials and the option to opt out of the short trainings. Surveys are under development and will be uploaded for IRB review prior to sending out to participants.

*Training observation:*

A study team member will sit quietly during the in person trainings, and will listen and observe what happens, and take jottings or notes. The study team will not collect PHI and no identifiers will be recorded. The observers' field notes will focus on training content, questions, and discussion. Following the training, the researcher will type and prepare detailed fieldnotes. The original jottings will be destroyed after the final typed fieldnotes are prepared.

*Online Training/Education:*

The Melanoma Toolkit for Early Detection (MTED) is a Continuing Medical Education training that PCPs from the intervention arm of the study will be encouraged to complete as part of the intervention. Participants will be provided with a link by email to complete the training within the online platform. The Toolkit contains various Epic tools (SmartPhrases, the melanoma risk stratification framework, a skin cancer-specific after visit summary) and a self-paced online curriculum (see IRB #19372 – “Educational Program for the Early Detection of Melanoma in Oregon”). A separate copy of the online curriculum and surveys has been made specifically for this study to avoid cross-contamination of data. Knowledge will be assessed among the intervention participants as pre-post intervention evaluations. Knowledge and confidence assessments are embedded in the online learning MTED modules (as pre- and post-test surveys) and have demonstrated improvement in PCP melanoma knowledge and confidence in a prior study (Orfaly 2021). This information will allow us to measure the level of uptake of the curriculum and track any changes in overall referral and biopsy numbers of Toolkit-trained PCPs. The data will always be assessed as an aggregate and never on an individual provider basis. Individual PCPs will be de-identified and will create a unique ID. Those who complete the MTED training can request CME upon completion.

*Interviews:*

The study team will conduct interviews from the two study sites. We will invite everyone who participated in the first training to the interviews. Interview will last up to one hour and will take place outside of regular work hours.

Using a semi-structured interview guide, the interviewer will ask participants questions designed to increase our understanding of approaches to screening for melanoma, current systems in place, barriers to implementation, perceptions around skin cancer training and education, uptake of training and how it influenced delivery of care. No personal health information (PHI) will be collected. Interviews will take place in-person, over the telephone or video all using an OHSU-approved platform. If Webex or GoToMeeting (videoconferencing) is used to record the conversation, the recording meeting file (MP4 video file format) will be converted to an audio-file (MP3), and the original file will be immediately destroyed. Audio-recording from interviews will be professionally transcribed. If video is recorded, we will convert the video file to be audio-only, share that audio with the transcriptionist, and destroy the original video file.

Subsequent interview guides will be informed by the participation in the multi-educational training opportunities and will be submitted for IRB approval before they are conducted.

**EHR Data:** The majority of data for this study will be drawn from the EHR to document clinician screening for skin cancer during routine primary care outpatient visits.

Data collection will include three main time periods: 12 months of baseline data; 2-3 months of active intervention; and 12 months of post intervention data.

For a subset of patients, we will obtain patients' MRN to conduct a chart review. De-identified data are insufficient to identify medical photography, which requires opening charts to review the photographs. Biopsy interpretation are also embedded in the patient's chart, which we will review. Any new EHR data will be linked through a separate crosswalk and scrubbed for analysis.

Table 1 includes the indicators from the EHR that will be collected to evaluate the impact of the intervention and other co-variates of interest and their data source.

Quantitative analytic data will include a study ID for clinicians so that we can determine exposure of the clinician to the intervention. No patient level identifiers will be used in this study.

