**Table 1**

Data Class	Examples include, but are not limited to:	Data source
Clinician characteristics	sex, age, degree (MD, DO, NP, PA, resident), years of practice	Public faculty data

Encounter information	Encounter date, encounter type, clinician ID, reason for visit, level of service, clinic ID, Department ID, encounter ICD9/10 problems, encounter CPT codes, encounter payor(s), skin cancer screening performed, use of skin cancer screening tool, use of SKLIP , biopsy performed, referral to dermatology, econsult to dermatology. Use of skin cancer dot phrase, Established vs. new patient.  Patient characteristics age, sex, race, ethnicity.	EHR, chart review
biopsy info/ pathology	Biopsy result, number of biopsies performed, number of skin lesions biopsies, Breslow thickness	EHR, chart review
Clinician knowledge and confidence	MTED pre- and post-evaluations,	From IRB approved Surveys ( IRB #19372 – “Educational Program for the Early Detection of Melanoma in Oregon” ).
practice pattern, referral practice	qualitative Interviews	Coded qualitative interview transcripts

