**8) Data Analysis**

Quantitative Data: Univariate descriptive statistics will be examined for all variables from the MTED pre- and post- evaluation survey. Comparison between data collection timepoints will be completed using Chi-square test (categorical), ANOVA (continuous), or Kruskal-Wallis one-way ANOVA test (continuous variables that are not normally distributed). Standard qualitative analysis techniques will be used for coding open-ended questions.

Descriptive statistics will be used to report screening, biopsy and referral characteristics at each data collection time points. Means, standard deviations will be reported for normally distributed continuous variables and medians and interquartile ranges (IQR) will be reported for non-

normally distributed ones. Frequencies and percentages will be calculated for categorical variables. The main comparison is between clinicians in the multicomponent educational intervention arm vs. clinicians at the same sites that do not have exposure to the multicomponent educational intervention. These two groups of clinicians are examined using a pre-post study design to evaluate outcomes including change in risk assessment, biopsy referral and identification of skin cancers. Linear mixed-effects regression models adjusting for clustering effects within study sites and other potential confounders will be used to compare the intervention and control arms in screening, biopsy and referral characteristics outcomes from baseline to post-intervention. A p-value < .05 will be considered statistically significant.

Qualitative data analysis: The study team will meet regularly to review fieldnotes and transcribed data and listen to and discuss key segments of the recorded interviews. Analyzing qualitative data as it is collected is crucial to monitoring data quality, refining interview guides, and monitoring theme saturation. This ongoing process will be used to track emerging themes and create a coding template to be used for more in-depth analysis. We will follow the 5-phase analysis strategy described by Miller and Crabtree (describing, organizing, connecting, corroborating/ legitimizing, representing). We will use an immersion-crystallization approach in which the team reads and discusses the data for each participant (immersion) to identify key findings (crystallization); first to identify key themes within each “case”, and then to identify cross-case findings.

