### b. Potential Benefits to Subjects

Clinicians exposed to the intervention may gain additional knowledge and expertise for diagnosing and managing skin cancers. Practice members who attend the group training in person will receive a lunch and participating clinics may receive at least 1 SKLIP dermoscopy device for every 2 clinicians in the intervention clinics. SKLIP devices may be kept by clinics at the conclusion of the intervention.

Participants who are invited and complete a one time interview will receive \$100 dollar Amazon gift card.

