Enhancing Skin Cancer Early Detection and Treatment in Primary Care

NCT05675709

March 1, 2025

Final approach to analysis

Analyses

We used descriptive analyses to examine participating clinician characteristics and rates of e-consults, dermatology referrals and biopsies performed (defined as the number of cases per 1000 patients). We conducted a paired t-test to evaluate change in knowledge scores and used generalized estimating equation-based (GEE) models with link function of Poisson distribution and an exchangeable correlation structure to compare referral outcomes. The models included exposure to training (Yes/No), pre- and post-training time periods and the interaction of these two indicators as predictors. All analyses were two-sided, statistical significance was set at type I error of 5% and analyses were conducted using R Statistical Software.

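### If lesion patients move to trained clinicians within the same two clinics, the SAP's training-by-period interaction cannot tell this from a training effect; a few added tables would show it

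*Protocol*

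**What the plan says.** - **Comparison.** Protocol section 8 states: "The main comparison is between clinicians in the multicomponent educational intervention arm vs. clinicians at the same sites that do not have exposure". Both groups are followed from before to after training. The outcomes named there include biopsy referral and identification of skin cancers, analysed with linear mixed models adjusted for site clustering and other confounders.
- **Final model.** The SAP fits a Poisson GEE with exchangeable correlation to referral outcomes: "The models included exposure to training (Yes/No), pre- and post-training time periods and the interaction of these two indicators as predictors". It lists no term for visit mix or case mix. Rates of e-consults, referrals and biopsies per 1,000 patients are descriptive. No rule says which clinician a patient or event belongs to.
- **Tools and workflow.** Protocol section 6 says of workflow: "We will support workflow restructure to involve use of Epic tools, SKILP devices, etc. but are unable to assess changes to workflow itself". Devices are handed out with lunch, "along with SKILP devices at the intial training and educational materials". The training "may be delivered to the entire healthcare team (nursing staff and medical assistants) to facilitate implementation". Section 10b adds that "participating clinics may receive at least 1 SKLIP dermoscopy device for every 2 clinicians in the intervention clinics".
- **Data to hand.** The encounter variables in Table 1 include "clinician ID, reason for visit, level of service".
- **Totals.** Protocol section 4 lists pre- and post-intervention counts among the primary endpoints, including total dermatology referrals. Section 8 plans descriptive statistics at each time point. Sections 2 and 5b name baseline data as a control. The SAP specifies no pooled before/after contrast.

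**The concern.** The two groups are colleagues in the same buildings. Once some of them have a dermoscopy device, new triage training and support to reorganise workflow, it would be natural for a patient with a suspicious mole to be booked with, or handed to, one of them. If the resulting referral or biopsy is credited to the clinician who saw the patient, it leaves the untrained group's numerator and enters the trained group's. The interaction is a ratio of two post/pre ratios, so it moves on both sides at once. The clinics could find no additional lesion while the interaction rises above 1.

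The study's hypothesis is that more skin cancers are diagnosed, and earlier. A positive interaction with a flat clinic total would not support that, and nothing in the SAP prompts the reader to check.

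**Working it through.** The documents give no expected rate ratio or power calculation, so there is no planned figure to reproduce.

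**Inputs from the protocol**
- About 80 clinicians, about 40 of them trained (section 5a), so about 40:40.
- At most 200 biopsied patients a year in each clinic (section 5a): 2 × 200 = 400 a year, or 400 / 2 = 200 per group per period if the groups have equal volume.
- Patients a year from the printed totals of Tables 2 and 3: (6,251 + 4,737) + (6,670 + 5,012) = 10,988 + 11,682 = 22,670.
- Baseline rate: 400 / 22,670 = 17.6 per 1,000.

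**Assumed:** a share *s* of the untrained group's post-period lesion events moves to the trained group, events are credited to the clinician seen, and total detection does not change. The documents give no value for *s*.

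**False ratio.** With T trained and U untrained clinicians of equal volume:

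ratio = (1 + s·U/T) / (1 − s), which is (1 + s)/(1 − s) at 40:40.

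| s | Biopsied patients moved per year | Ratio, numerators only | Ratio if denominators move too | Clinic rate per 1,000 |
|---|---|---|---|---|
| 5% | 10 | 1.05/0.95 = 1.11 | 1.10 | 17.6 |
| 10% | 20 | 1.10/0.90 = 1.22 | 1.22 | 17.6 |
| 20% | 40 | 1.20/0.80 = 1.50 | 1.49 | 17.6 |

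At *s* = 10% the trained rate goes from 17.6 to 19.4 per 1,000 and the untrained rate from 17.6 to 15.9. The split matters: at 20 trained and 60 untrained the ratio is (1 + 0.10 × 60/20)/0.90 = 1.44; at 60 and 20 it is (1 + 0.10 × 20/60)/0.90 = 1.15.

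**Chance of a false p < 0.05 (two-sided), 40:40, s = 10%**
- Poisson approximation with N = 200 events per cell: z = ln(1.222)/√(4/200) = 0.2007/0.1414 = 1.42, which gives about 29%.
- The same test with denominators moved and the actual cell counts: 28%.
- Simulated Poisson GEE with exchangeable correlation: 22%. This assumed 80 clinicians, 5 events per clinician-year, a between-clinician CV of 0.7, a within-clinician period CV of 0.3 and 1,000 runs. Its rejection rate at *s* = 0 was already 7%.
- At *s* = 5% the Wald and GEE figures are 11% and 9%; at *s* = 20% they are 80% and 64%.
- At half the ceiling (N = 100), z = 0.2007/√(4/100) = 1.00, about 17%.

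These figures use biopsy counts because the documents give no referral counts, although referrals are what the SAP models.

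**What the fitted model would show.** The exponentiated period coefficient is the untrained group's own post/pre ratio: 0.90 at *s* = 10% with no trend. Period plus interaction gives the trained group's: 1.10. Their ratio is 1.10/0.90 = 1.22, and the pooled ratio is (1.10 + 0.90)/2 = 1.00.

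**The case against.** The strongest reply has five parts.

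- **No document describes patients being moved between clinicians.** The workflow sentence is about Epic tools and devices. This stands: the mechanism is possible, not shown. A reader might infer that steering occurred, or that a positive interaction would be an artefact. The documents support neither.
- **Devices also go to the clinics, and whole teams may be trained.** This weakens the incentive to re-route and exposes untrained clinicians to the tools. Such spillover pulls the interaction towards 1 and may offset part of the shift. It does not make the interaction easier to read, because neither effect is measured.
- **The pattern is not invisible.** A reader might infer that the plan has no clinic total and no way to see re-routing. That goes too far. The protocol foresees pre/post totals and descriptives, group counts can be summed, and the untrained trend can be read from the period coefficient. The interviews also ask how training affected care delivery. What is missing is a stated intention to report these results beside the interaction and read them together.
- **The SAP's interaction model covers referral outcomes only.** This stands. Extending it to biopsy referral or identification of skin cancers rests on protocol section 8, which used a different model with confounder adjustment.
- **The study is mainly about feasibility, and the protocol admits that workflow change cannot be assessed.** This supports treating the point as an improvement rather than a flaw that undermines the trial.

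A reader might also assume larger counts: 500 events per cell would give 61% at a 10% shift. The only event count in the documents implies about 200 per cell, for biopsies, so the lower figures are the ones to use.

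**Conclusion.** The point holds as a cheap improvement. With comparators in the same clinics, unassessed workflow change and a model limited to training, period and their interaction, a net movement of lesion patients towards trained clinicians would be indistinguishable from a training effect on the interaction alone.

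This rests on events being credited to the clinician seen. Had patients been assigned to their baseline clinician, re-routing would not shift the rates, but no assignment rule is given. The ratios and error rates in the working illustrate an unknown *s*, with equal groups and no net change; they do not estimate what happened in this study.

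**What to change.** Beside the interaction, report:

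1. The pooled pre/post rate across trained and untrained clinicians, and each group's own post/pre ratio. A rise in the trained group with a matching fall in the untrained group and a flat total should be read as a sign of re-routing.
2. The share of skin-complaint visits, from reason for visit and clinician ID in Table 1, that go to trained clinicians in each period.
3. As sensitivity analyses only: (a) the GEE with patients assigned to their baseline clinician, where one can be identified; (b) the GEE in visits whose reason is not a skin complaint. The second reduces re-routing but does not remove it. An untrained clinician may notice a mole at an unrelated visit and pass the patient on, and training may change how visits are labelled.

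State the rule that assigns patients and events to clinicians.

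Use the pooled rate to qualify the interpretation, not as a condition for claiming an effect. It is an uncontrolled before/after contrast, open to secular trend, and it dilutes a true effect: with half the clinicians trained, a real ratio of 1.22 among them becomes (1.22 + 1.00)/2 = 1.11 overall.

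The cost is a little more analysis from variables already listed, reported at group level, with wider intervals in the two restricted analyses. Because the SAP describes its analyses in the past tense, label these as additions.

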## 4) Study Design

This study is a mixed method pilot study to determine whether multicomponent education module improves the ability of Primary Care Providers (PCPs) to identify and triage skin cancer. The main independent variable is the multicomponent education for clinicians. This is primarily a feasibility study to evaluate the engagement and uptake of the training and change in skin cancer screening behavior on the part of clinical teams. We hypothesize that exposure to the intervention will increase clinician knowledge, increase the use of a SKLIP dermoscopy device to facilitate capture of high-resolution dermoscopy images, and increase screening for skin cancer.

Outcomes:

- Uptake of the training and performance of skin cancer screening processes measured by proportion of clinicians invited to participate in the educational intervention that complete the training modules; use of the Epic smart tool and dotphrases.
- Clinical knowledge measured through pre- and post-tests implemented during live (in-person or virtual) training.
- Use of the risk assessment tool measured through EHR data.
- Identification of suspicious lesions measured through EHR data.

We hypothesize that the multicomponent education strategy will result in the diagnosis of more skin cancers at earlier stages. Primary endpoints of the study include the pre- and post-intervention: number of melanomas biopsied, mean and median Breslow depth of melanomas biopsied, number of other malignant skin tumors biopsied, total number of referrals to dermatology, number of referrals to dermatology for concerning moles, and number of OHSU PCPs who access the Melanoma Toolkit for Early Detection (MTED), an online Continuing Medical Education training. There will be two comparison groups: OHSU PCPs receiving the intervention, OHSU PCPs not exposed to the intervention.

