**b) Inclusion and Exclusion Criteria**

Two OHSU primary care clinics will be assigned to receive exposure to the melanoma early detection intervention. Baseline data and clinicians at the two clinics who do not receive the intervention will serve as study comparators.

We will be using secondary EHR data from the study clinics. Biopsy and referral data will be extracted from EHR from patients within these two primary care clinics who were screened, referred, biopsied for potential skin cancer and/or diagnosed with melanoma. Data from all other patients seen in these clinics during the time period will be included for comparison. These data will be electronic health record (EHR) data from patients between the ages of 18 and 110 with an encounter in one of the study clinics. A subset of this data will undergo a chart review to affirm use of specific devices to photograph lesions and free text biopsy results and/or interpretation.

We may observe all in-person trainings. There are no inclusion/exclusion criteria for training observation. All training participants will be 18 years or older and are required to speak English during the training and in their occupations.

Qualitative interviews will be conducted with clinicians who receive the intervention. These individuals are all aged 18 years or older and all practice members speak English. No patients will be interviewed for this research.

Exclusion criteria: No one will be intentionally excluded.

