**e) Recruitment Methods**

Study staff will submit an inquiry for research engagement per the Department of Family Medicine's current Standard Operating Procedure. DFM research leadership and clinic leadership will confirm the participation of each clinical site. Then, with clinic leadership support, advanced providers from each site will be invited to participate in the multicomponent educational intervention.

We will email leaders at each of the sites and ask for permission to observe the trainings and take fieldnotes. A reminder invite to the in-person training will be shared with clinic leadership, and will be emailed to the participating clinic members (see recruitment materials). This email will remind participating clinic members of the upcoming training and include and a copy of the information sheet. During the live training, we will ask participants for their email addresses so that we may remind them to complete the training post-test and to invite them to complete the online portion of the trainings. (See supplemental materials).

Patients are not being directly recruited to this study however, patient level EHR data will be used to evaluate the impact of the intervention as outlined in the primary endpoints above.

We will invite and potentially interview all clinicians but will stop once saturation is reached and no new information is being gleaned. In exchange for participation in the one hour interview, clinician member participants will receive a \$100 Amazon gift card.

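### Could clinicians who only watched the recorded training be counted as unexposed, and does the plan need to change for that?

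*Protocol*

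**What the plan says.** Protocol section 4 (Study Design) states: "The main independent variable is the multicomponent education for clinicians". Section 5b sets the comparison: "Baseline data and clinicians at the two clinics who do not receive the intervention will serve as study comparators".

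Section 6 (Group Training) allows live sessions to be in person or virtual, and then adds: "A pre-recorded version of the trainings will also be available to accommodate busy schedules". On attendance it says: "We will use a sign-in sheet to collect names and email addresses of those who attended the in-person trainings". The stated purposes of that sheet are to "provide a link to the online portion of the trainings and to measure expose of the training".

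Three other places bear on who can be identified as trained:

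- Section 5e (Recruitment Methods): "During the live training, we will ask participants for their email addresses so that we may remind them to complete the training post-test".
- Section 6 (Refresher trainings): "We will email all participants of the intial training and offer the refresher materials".
- Section 6 (EHR Data): "Quantitative analytic data will include a study ID for clinicians so that we can determine exposure of the clinician to the intervention".

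The SAP describes GEE models with exposure to training (yes or no), period, and their interaction. It does not say which component, format or source record makes a clinician exposed. It is dated March 1, 2025 and written in the past tense.

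**The concern.** The exposure-by-period interaction carries the main comparison, so the exposure variable has to be right. The training could be received by three routes, and a record meant to measure exposure is named for only one of them. Virtual attendees can probably be traced through the email addresses taken at live sessions. For the recording, no viewing log, registration or named link is described.

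The comparators work in the same two clinics, and all eligible clinicians there were invited. The natural users of a recording offered for busy schedules are invited clinicians who missed the live session. If exposure were coded from live attendance alone, those clinicians would be comparators who had in fact been trained. Provided the recording works and they otherwise resemble the other comparators, the interaction would shrink toward no effect. A reader of a null result could not tell that from a training that does nothing.

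**Working it through.** The plan has no power calculation or effect size for this comparison, so there is no figure to reproduce. The check has two parts.

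**What the text commits the analysts to**

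- The sign-in sheet is given the purpose of measuring exposure, but it is not called the only source.
- The EHR Data paragraph says exposure will be determined by clinician study ID. It names no source record, and it does not restrict the determination to in-person attendance.
- One outcome in section 4 is the share of invited clinicians who complete the training modules. That needs completion counted against the invitation list. It does not name the recording and may refer to the online modules.
- The refresher emails go to those who completed the initial training, which implies a list of completers. Whether watching the recording counts is not stated.
- The recording covers the trainings in the plural, after an initial and a refresher session have been described. A clinician who attended the first session live and watched a recorded refresher is already exposed. Only someone who attended no live session is at issue.

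Coding recording-only clinicians as unexposed is therefore one possible reading, not a rule in the plan.

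**How large the dilution could be**

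Inputs:

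- Comparator size C: about 40, from section 5a (about 80 clinicians less about 40 recruited). Section 5a also speaks of up to 40 per site and about 40 at each training, so C could be smaller.
- True interaction rate ratio RR = 1.5 (assumed).
- Number of recording-only clinicians k (assumed), with share m = k/C.
- Response f to the recording, as a fraction of the log effect (assumed).
- Equal patient volume per clinician and no other difference in time trend (assumed).

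Formula: observed RR = RR / (1 − m + m × RR^f).

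For 4 of 40, m = 0.10:

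- Full response (f = 1): 1.5 / (0.90 + 0.10 × 1.5) = 1.5 / 1.05 = 1.43. Log effect kept: ln 1.4286 / ln 1.5 = 0.88.
- Half response (f = 0.5): RR^0.5 = 1.2247, so 1.5 / (0.90 + 0.12247) = 1.5 / 1.02247 = 1.47. Log effect kept: 0.945.

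Other shares by the same formula:

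| Share of comparators (m) | Example | Observed RR, f = 1 | Observed RR, f = 0.5 |
|---|---|---|---|
| 0 | none | 1.50 | 1.50 |
| 0.10 | 4 of 40 | 1.43 | 1.47 |
| 0.20 | 8 of 40, or 4 of 20 | 1.36 | 1.44 |
| 0.40 | 4 of 10 | 1.25 | 1.38 |

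The documents support no row over another, including the first.

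The direction is not fixed either. If recording-only clinicians have their own time trend t relative to other comparators, the denominator becomes 1 − m + m × t × RR^f. Dilution disappears once t falls below 1/RR^f, which is 0.67 for full response and 0.82 for half.

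**Would counting any mode as exposed help?**

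Move the 4 clinicians into the exposed group, giving 44 exposed and 36 clean comparators. With full response the ratio returns to 1.50. With half response it is (40 × 1.5 + 4 × 1.2247) / 44 = 64.899 / 44 = 1.475, against 1.467 if they stay as comparators. Reclassifying partly trained clinicians then mostly moves the dilution from one group to the other.

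**The case for a change.** The best case for acting is that the exposure term is the predictor of interest, a coding rule has already been applied, and the reader cannot see it. The clinician study ID links a clinician to EHR data but names no source for exposure. The other records described do not obviously fill the gap. The pre- and post-tests are tied to the in-person session, the online toolkit uses a self-created ID, and names given for CME credit are not linked to it. The study is a feasibility pilot, but the protocol still calls exposed versus unexposed clinicians its main comparison and tests at 5%. Uptake is itself an outcome. A definition costs one sentence, and a roster check covers only about 80 people.

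Most of that stands as description. The SAP gives no definition, and no access record for the recording is described. What does not follow is that the plan must change:

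- The proposed rule, attendance by any mode, is one defensible choice among several. Section 8 defines the comparator by lack of exposure to the multicomponent intervention. Dermoscopy devices were to be given out at the initial training, and the sign-in sheet was used to send the online link. Someone who only watched a recording may have missed both.
- A sensitivity analysis that recodes or excludes these clinicians needs viewing data that may never have been kept.
- The supplemental materials, which the protocol cites for the training emails, were not available here and may describe tracking.

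**Conclusion.** No change to the plan. This is a gap of detail that analysts have to settle when they build the exposure variable, and the protocol gives them a route through the clinician study ID. The concern needs three things that the documents do not show: that some clinicians had only the recording, that they were coded as unexposed, and that this coding is wrong for a comparator defined by the multicomponent intervention.

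The size is correspondingly uncertain. At the comparator count that section 5a most directly supports (about 40), 4 recording-only clinicians and an assumed rate ratio of 1.5 would give 1.43 with full response or 1.47 with half, keeping 88% to 95% of the log effect. A larger share would dilute more and a share of zero not at all. In a study that the protocol calls primarily a feasibility study, with no power claim, a null interaction would not be decisive in any case.

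When the results are written up, one sentence on how exposure was assigned for in-person, virtual and recording-only clinicians is ordinary reporting. If recording access was not logged, possible contamination of the comparator belongs among the limitations. Neither alters the model or the comparison.
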